There are several reports regarding the effects of Ramadan fasting on the human metabolism. Fasting leads to a decrease in serum glucose, insulin, lactate, and carnitine, as well as an increase in free fatty acids, hydroxy butirate, cholesterol, and triglyceride levels. As we know, maternal glucose infusion causes stimulation of short-term fetal activity and uteroplacental blood flow is essential for fetal development and wellbeing (*Osol, 2009*).

During the month of Ramadan, healthy adults abstain from food and drink from dawn to sunset. Pregnant are allowed, if they choose, to postpone the fast until after delivery. However, most of the women would like to fast with their families rather than doing this alone later. Therefore, most Muslim pregnant women fast during the holy month of Ramadan. Consequently, diet restriction and fasting could adversely affect pregnancy outcome, especially if Ramadan

*The Effect of 3rd trimester Ramadan fasting on Obstetric outcome
(Study Protocol)*

falls during the hot summer months with long days of fasting
(Mirghani, 2006).

Aim of the Work

This study aimed to find out the association between fasting during Ramadan and obstetric outcome in third trimester regarding to hypoglycemic symptoms, fetal growth, AFI, mode of delivery, birth weight and neonatal outcome.

Study question:

In pregnant women in the third trimester, does fasting during the holy month of Ramadan has a poor obstetric outcome regarding to hypoglycemic symptoms, fetal growth, AFI, mode of delivery, birth weight and neonatal outcome?

Patient and Methods

Type of the study :

Prospective Comparative Cohort Study.

Study setting :

EL- Demerdash outpatient clinic.

Duration of the setting :

The Holy month of Ramadan (from 18th June To 16th July 2015. Avenge hours of fasting 16 hours.

Population (study will include):

The patients will be recruited from outpatient clinic during Ramadan then followed during the holy month then grouped into three groups A ,B, C regarding fasting state and each group contain 53 patient after exclusion drop out patient

A- Non fasting group

B- Partially fasting group (average days of fasting 10-20 day).

C- Totally fasting group

Inclusion criteria:

- *Within the range of 20 – 35 years.*
- *3rd trimester pregnancy (starting from 28 weeks) which is going to be calculated according to the date of the last menstrual period & confirmed by ultrasonography.*

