- *Normal healthy women with average body mass index (BMI). Normal range (18.5 to 25).*
- *Women included have no medical disorder.*

Exclusion criteria :

- *History of systemic disorder.*
- *Smoking narcotics or alcohol use.*
- *Have previous history of fetal loss.*
- *Multiple pregnancies.*

Methodology

Women who fulfilled the eligibility criteria are going to be subjected to:

1) Complete history taking:

- a. Personal history.*
- b. Medical history.*
- c. Obstetric history.*
- d. History of present pregnancy: with special emphasis on signs & symptoms of hypoglycemia in the form of fatigue, dizziness, fainting, blurred vision, vomiting.*
- e. Fetal kicks.*

2) General examination: assessment of vital data.

3) Ultrasound fetal biometry every 2 weeks till delivery looking for

- **Fetal biometry.**
- **AFI (ammonic fluid index)**
- **Doppler.**

4) Fetal weight after delivery.

Sample Size Justification:

*The required sample size has been calculated using the G*Power Software (Universität Düsseldorf, Germany).*

The primary outcome measure is the difference between the three study groups as regards the fetal birth weight. The secondary outcome measures are the incidence of unwanted fetal outcomes (e.g., IUGR, PTL, or NICU admission).

Since there is currently no adequate information regarding the outcome measures in patients who are fasted for the whole or part of the month, the current exploratory study would target an effect size that could be clinically relevant.

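### Hypoglycaemic symptoms are an outcome in the aim, but the plan specifies them only within the history of the present pregnancy, with no recall window, link to fasting days or repeat

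*Combined protocol and SAP*

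**What the plan says.** In the combined protocol and SAP, Aim of the Work says the association with fasting will be studied "regarding to hypoglycemic symptoms, fetal growth, AFI, mode of delivery, birth weight and neonatal outcome", and the study question repeats that list. Under Sample Size Justification, birth weight is the primary outcome. The secondary outcomes are unwanted fetal outcomes, with IUGR, PTL and NICU admission as examples. Maternal symptoms are not named there.

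The Methodology section opens its list of assessments with "Women who fulfilled the eligibility criteria are going to be subjected to". Symptoms appear once in that list, at item 1d, the history of the present pregnancy, "with special emphasis on signs & symptoms of hypoglycemia in the form of fatigue, dizziness, fainting, blurred vision, vomiting". Fetal kicks follow as item 1e. The only assessment with a stated interval is item 3, "Ultrasound fetal biometry every 2 weeks till delivery looking for", and it covers biometry, AFI and Doppler.

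Under Population: "The patients will be recruited from outpatient clinic during Ramadan then followed during the holy month then grouped into three groups". The partially fasting group is defined by an average of 10 to 20 days fasted, so group membership depends on the whole month. The study period is given as "The Holy month of Ramadan (from 18th June To 16th July 2015".

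**The concern.** A symptom outcome for a fasting study has to refer to the time when women were, or could have been, fasting. A history of the present pregnancy refers to the pregnancy so far. Fatigue, dizziness and vomiting in earlier months cannot be effects of a fast that had not begun, yet under item 1d they would count the same as symptoms on a fasting day. Symptoms after the history have no specified place to be recorded.

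There is also a route from symptoms to exposure. The introduction says that some pregnant women do not fast because of possible harm to the fetus, and that perceived harm to mother or fetus is seen as the reason not to fast. Women who had symptoms before Ramadan may therefore be over-represented in the non-fasting group. Without a separate pre-Ramadan record, this can be neither seen nor adjusted for.

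At stake is whether the symptom comparison, part of the study's own question, can be interpreted at all.

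**Working it through.** **The plan's own figures.** The plan gives no calculation for symptoms. Its other figures reproduce and do not bear on this point. One-way ANOVA with 53 per group, alpha 0.05 and 0.25 read as Cohen's f gives 80.5% power (stated 80%). The chi-squared test with w = 0.3, N = 159 and 2 degrees of freedom gives 93.3% (stated 93%).

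**Inputs from the documents.** Eligibility from 28 weeks by last menstrual period, that is 28 × 7 = 196 days. Ramadan from 18 June to 16 July, 29 days inclusive. Scans every 14 days. 53 women per group.

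**1. Share of the history window before Ramadan.** A woman at 28 weeks or more with at most 29 Ramadan days behind her has at least 1 − 29/196 = 85% of the window before Ramadan. This is calendar time, not a share of symptoms, and dating from the last period includes some days before conception.

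**2. Share of Ramadan after the history.** Assume the history is taken on enrolment day e. The share of the month still to come is (29 − e)/29:
- day 1: 28/29 = 97%
- day 8: 21/29 = 72%
- day 15: 14/29 = 48%
- day 22: 7/29 = 24%
- day 29: 0%

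With even enrolment over the month (an assumption; the plan gives no pattern) the average is 14/29 = 48%. Early recruits lose most of the month; late recruits report most of it, but mixed with earlier months.

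**3. Illustration of the mixing, under assumed rates.** Suppose 10% of non-fasting and 30% of fasting women have symptoms during Ramadan, all of them captured, and a fraction q had such symptoms earlier, independently. The recorded rate is 1 − (1 − q)(1 − r), where r is the Ramadan rate. Power is for a two-sided two-proportion test at 0.05 with 53 per group.

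| q, same in both groups | non-fasting | fasting | gap (points) | power |
|---|---|---|---|---|
| 0 | 10% | 30% | 20 | 74% |
| 20% | 28% | 44% | 16 | 40% |
| 40% | 46% | 58% | 12 | 23% |
| 60% | 64% | 72% | 8 | 14% |

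None of these rates comes from the documents. The plan compares three groups, and the table leaves out the loss in step 2.

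**4. Direction.** If q differs between groups, the same formula moves the gap either way:
- q = 40% in non-fasting and 20% in fasting women: 1 − 0.6 × 0.9 = 46% against 1 − 0.8 × 0.7 = 44%, so the sign reverses.
- q = 20% in non-fasting and 40% in fasting women: 1 − 0.8 × 0.9 = 28% against 1 − 0.6 × 0.7 = 58%, a gap of 30 points, larger than the true 20.

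**5. Coverage by repeat visits.** If symptoms were repeated at 14-day scans but stopped at the end of Ramadan, a woman enrolled on day 15 would be seen again on day 29, but one enrolled on day 16 not until day 30. Enrolment days 16 to 29 are 14 of 29, or 48% of women under even enrolment, with no follow-up symptom visit. Scans continue until delivery, so the first scan after Ramadan can cover them.

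**The case against.** The strongest reply is that silence is being read as a rule. The Methodology list ends with weight after delivery, so it spans the whole study and is not a description of one visit. Vital signs have no stated frequency either, and fetal kicks under the same history heading could suggest ongoing monitoring. The study is prospective, and women are "then followed during the holy month then grouped into three groups", which is compatible with repeated questions about symptoms. This stands to a degree. A reader might infer that symptoms are asked once, at entry, and never again; the documents use no such words, and only the absence of any specified later collection can be claimed. It does not remove the point. Even a repeated history of the present pregnancy, with no recall window, would not separate fasting days from earlier months.

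Second, symptoms are neither the primary nor a named secondary outcome, carry no power claim, and belong to a study that calls itself exploratory. A reader might take their first place in the aim as a sign of rank, but list order does not show that. The objection limits the weight of the point; symptoms are still part of the stated question.

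Third, a reader might infer that the flaw makes fasting look safer. That follows if earlier symptoms are equally common in all groups, or commoner among women who then do not fast. The documents establish neither. Women also know whether they are fasting, and reporting could differ in either direction.

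**Conclusion.** The point holds as a defect in how a stated outcome is measured. As written, the symptom data combine pre-Ramadan pregnancy symptoms with fasting-period symptoms, carry no link to days fasted, and have no specified capture after the history. A comparison across the three groups could not be attributed to fasting.

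The firm figure is that at least 85% of a whole-pregnancy window lies before Ramadan. The 48% of the month falling after the history rests on a history taken at enrolment and on even enrolment. The loss of power from 74% to between 40% and 14% is an illustration under assumed rates, independent periods and a two-group test. No direction of bias is claimed, and the birth-weight comparison is untouched.

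**What to change.** Amend Methodology item 1 and the data form as follows.

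- **At enrolment**, record the listed symptoms and fetal kicks separately for (i) the pregnancy before Ramadan and (ii) the Ramadan days so far, with the number of days fasted.
- **At each planned two-weekly scan**, repeat the same checklist for the period since the last visit, with days fasted in that period. Continue through the first scan after Ramadan ends, or to delivery if that comes first, so that late recruits are covered. At that last checklist, keep Ramadan days apart from later days.
- **In the analysis**, compare symptoms during Ramadan, including Ramadan days before enrolment, across the three groups. Adjust only for the pre-Ramadan symptoms. The undivided history should not serve as a baseline: it contains fasting days, so adjusting for it would remove part of the effect sought.

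The cost is a few minutes at visits already planned and one extra form page, with no added visit or test. Some recall error will remain for days before enrolment. Self-selection into fasting and unblinded self-report also remain and should be stated as limitations.

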So, it is estimated that a sample of 53 patients in each study group (total 159 patients) would achieve a power of 80% (type II error, 0.2) to detect a statistically significant difference among the three groups as regards the fetal birth weight for a medium effect size (eta squared, η^2) of 0.25. The effect size (eta squared, η^2) is calculated as follows: $\eta^2 = \text{between-group sum of squares} / \text{total sum of squares}$. This calculation used a two-sided F test with a numerator degree of freedom ($k-1$) of 2, a denominator degree of freedom ($n-k$) of 156, and a confidence level of 95% (type I error, 0.05), where k is the number of groups and n is the total sample size. This sample size of 159 patients would achieve a power of 93% (type II error, 0.07) to detect a statistically significant difference among the three groups as regards the secondary outcome measures (IUGR, PTL, and NICU admission) for a medium effect size (w) of 0.3. The effect size (w) is calculated as follows: $w = \sqrt{(\chi^2/N)}$, where χ^2 is the chi-squared statistic and N

is the total sample size. This calculation used a two-sided chi-squared test with a confidence level of 95% (type I error, 0.05).

A medium effect size of $\eta^2 = 0.25$ or $w = 0.3$ for the primary or secondary outcome measures, respectively, has been chosen as it could be regarded as a clinically relevant difference to seek in this exploratory study.

Assuming an expected drop-out rate of approximately 10%, a total sample size of 180 patients (60 patients per group) will be recruited.

Statistical Methods:

Data will be collected, tabulated, then analyzed using IBM© SPSS© Statistics version 22 (IBM© Corp., Armonk, NY).

Normally distributed numerical data will be presented as mean and SD, and skewed data as median and interquartile range. Qualitative data will be presented as number and percentage. Comparison of normally distributed numerical data will be done using one-way analysis of variance (ANOVA). Skewed data will be compared using the Kruskal Wallis test. Categorical data will be compared using the chi-squared test, or Fisher's exact test when appropriate. A two-sided p-value <0.05 will be considered statistically significant.

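### Fetal growth and AFI are stated aims measured by serial scans, but the plan names no scan, per-woman summary or gestational-age adjustment for comparing them

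*Combined protocol and SAP*

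**What the plan says.** Aim of the Work lists the outcomes of interest as "regarding to hypoglycemic symptoms, fetal growth, AFI, mode of delivery, birth weight and neonatal outcome", and the Study question repeats them. Methodology, item 3, schedules "Ultrasound fetal biometry every 2 weeks till delivery looking for" three things: biometry, AFI and Doppler.

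The women do not share a starting point. Inclusion criteria admit "3rd trimester pregnancy (starting from 28 weeks) which is going to be calculated according to the date of the last menstrual period", with no upper limit. Under Population, "The patients will be recruited from outpatient clinic during Ramadan then followed during the holy month then grouped into three groups" according to how much they fasted. Scan number *n* is therefore neither a common gestation nor a common amount of fasting, and nothing in the design balances gestation across groups.

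For numerical data, Statistical Methods gives two tests. One is ANOVA on normally distributed data; for the rest, "Skewed data will be compared using the Kruskal Wallis test". It names no scan, change, slope, z-score, repeated-measures method or covariate. Gestational age appears only as an entry criterion.

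Sample Size Justification makes birth weight primary and gives IUGR, PTL and NICU admission as examples of secondary outcomes. Serial biometry and AFI are not named there.

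**The concern.** Both planned tests need one value per woman, and the plan does not say which. Two of the stated aims therefore have no defined numerical comparison, and the scan could be chosen after the data are seen.

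The choice matters because biometry rises steeply with gestation. A raw measurement at one scan is size at whatever gestation the woman had reached. Across women, gestational spread then enters the comparison as noise and can hide a real difference in growth. Women also choose whether to fast, and that choice may depend on how advanced the pregnancy is. Any resulting difference in mean gestation between groups would look like an effect of fasting.

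**Working it through.** The plan gives no power or effect figure for growth or AFI, so there is none to reproduce. The check is an illustration for estimated fetal weight.

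**From the documents:** three groups of 53; two-sided 0.05; entry from 28 weeks; scans 14 days apart; Ramadan 18 June to 16 July, which is 29 days.

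**Assumed:** entry spread evenly over 28–36 weeks; linear growth *g* and SD at fixed gestation *s* of (150 g/week, 400 g), (200, 300) or (250, 250); even recruitment over days 1–28; within-woman correlation 0.5–0.7; women past 40 weeks at the later scan dropped in the simulations.

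**1. The choice of scan is not trivial.** If delivery is at 40 weeks, a woman entering at 28 weeks has 7 scans and one entering at 38 weeks has 2.

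**2. Noise.** At a given visit number, gestation has variance 8²/12 = 5.33 weeks². The raw variance is 5.33*g*² + *s*², which is 1.75 to 6.33 times *s*².

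**3. Bias, no fasting effect, same visit number.** With one group *d* weeks further on, the F test (2 and 156 df) has noncentrality λ = 53 × (2/3) × (*gd*)² / (5.33*g*² + *s*²). Rejection is 10.6–16.6% at *d* = 0.5 and 30.1–54.3% at *d* = 1.

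**4. Bias, first scan on or after 16 July.** Simulated rejection is about 5% with no imbalance, 7–10% at 0.5 week and 15–25% at 1 week. These are lower than in step 3 partly because the 40-week cut removes women only from the more advanced group. The linear model adjusted for the entry value, gestation at entry and the interval between scans stays at about 4–6%.

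**5. Power if one group grows 40 g/week slower (assumed), no imbalance.** Recruits on days 1–14 reach the later scan 4 weeks after entry, and recruits on days 15–28 reach it after 2 weeks. The mean interval is 3 weeks with variance 1, so gestation at that scan has variance 5.33 + 1 = 6.33. The raw SD is √(6.33*g*² + *s*²), which is 550 g at (150, 400) and 677 g at (250, 250).

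The deficit Δ depends on when slowing starts. From the entry scan it averages 40 × 3 = 120 g. Throughout Ramadan (28 days from 18 June to 16 July) it is 40 × 4 = 160 g. With λ = 53 × (2/3) × Δ²/SD² = 35.33 Δ²/SD²:

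- Raw, from entry: λ = 1.68 and 1.11, power 19% and 14%.
- Raw, throughout Ramadan: λ = 2.99 and 1.97, power 32% and 22%.
- Adjusted for gestation at the scan (SD = *s*), from entry: λ = 3.18 and 8.14, power 33% and 72%.
- Adjusted for gestation at the scan, throughout Ramadan: λ = 5.65 and 14.47, power 55% and 93%.

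The first and third columns below are simulated for all rows except the second, which is the closed form above.

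| Analysis | Slowing from entry | Slowing throughout Ramadan |
|---|---|---|
| Raw ANOVA (simulated) | 14–22% | 21–35% |
| Model with gestation at the scan (closed form) | 33–72% | 55–93% |
| Model with the entry value added (simulated) | 42–95% | 42–87% |
| z-score change from entry (simulated) | 34–91% | 17–59% |

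**6. Why z-score change can lose.** With even recruitment, the entry scan follows 14 days of Ramadan on average, so subtracting it removes part of the effect. For a recruit on day *r* from 15 to 28, only (29 − *r*) of the 14 interval days lie in Ramadan, on average 7.5/14 = 54%. At (150, 400), with slowing throughout Ramadan, z-score change does worse than raw ANOVA.

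No effect was quantified for AFI or Doppler.

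**The case against.** A reader might infer that the plan tests raw biometry, or that its tests are invalid. The documents support neither. Statistical Methods does not say raw values will be used, and ANOVA on one gestation-standardised value per woman would be valid and would fit the wording. The defect is that the variable is left open; the consequences above are conditional on raw values being used.

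A reader might also infer that the groups do differ in gestation. The documents give no gestational age by group, and with no imbalance the type I error is about 5%.

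A third tempting inference is that z-score change from the entry scan is the obvious and much more powerful remedy. That holds only if slowing begins at each woman's entry scan. Recruitment runs through Ramadan, so the entry scan may already follow fasting.

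It is also fair to say that IUGR incidence gives growth a categorical comparison by the planned chi-squared test, and that the study describes itself as exploratory. Both limit the weight. But IUGR is not defined and does not cover AFI or Doppler, and exploratory status does not supply the missing variable.

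**Conclusion.** The point stands in conditional form. Two stated aims rest on serial scans at mixed gestations, and the plan names neither the value to compare nor an adjustment for gestation. If raw biometry is tested, the comparison is of size at mixed gestations. It has little power and is open to false findings from gestational imbalance.

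The sizes rest wholly on the assumed growth rates, SDs, entry range, recruitment pattern and imbalance, and they apply to estimated fetal weight only. Across those assumptions, adjusting for gestation beat raw ANOVA whichever way slowing was timed. Whether adding the entry value helps depends on that timing, which the documents cannot settle.

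The weight is low to moderate. Growth and AFI are not listed primary or secondary outcomes, and the birth-weight analysis and sample size are untouched.

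**What to change.** In Statistical Methods, pre-specify for biometry, AFI and Doppler:

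- **Value:** one per woman, from the first scan on or after 16 July.
- **Main comparison:** a linear model with group and gestational age at that scan (equivalently, gestation at entry plus the interval between scans), reporting group differences with 95% CIs.
- **Stated second version:** the same model with the entry-scan value added, noting that this scan may already follow fasting. Say how a woman whose entry scan falls on 16 July is handled, since one scan would then serve as both.
- **Acceptable alternative:** where a reference exists, a gestational-age z-score at the later scan, compared by the planned ANOVA or Kruskal-Wallis.
- **Sensitivity only:** z-score change from entry, noting that it subtracts an exposed baseline and that much of the interval falls after Ramadan for late recruits.
- **Report by group:** gestational age at entry and at the analysed scan, days of Ramadan before entry, the interval between scans, and the number of women without a later scan.

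The cost is SAP wording and a little extra analysis, with no new data. Women who deliver before the later scan are lost to this comparison, the z-score option requires choosing a reference, and other confounding between self-selected groups remains.

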Concurrence of fasting with pregnancy as a physiological condition introduces some controversies regarding the condition of the mother and the fetus. Pregnant women are exempt from fasting if it poses a risk to the fetus; however, many still fast while others are more cautious about its practice. Many pregnant show great interest in fasting and are able to perform this religious practice; however, they are concerned about their fetus and inquire about the possible associated complications during pregnancy According to the statics, in West Africa, 90% of pregnant women fasted during the month of Ramadan. The prolonged hunger presents itself as hypoglycemia or hyperketonuria, which may affect the neonatal weight, neonatal mortality and disability. During fasting, pregnant and breastfeeding women experience changes in metabolism, sleep patterns and daily physical activity (*Cuningham et al., 2010*).

Most Muslims observe Ramadan every year. Exemption from fasting is permitted for women who are pregnant or breastfeeding, but the missed fasts must be completed before the next Ramadan (**Rashed, 2010**).

Muslim women choose to fast during pregnancy because of a sense of religious duty, familial support, positive views on fasting, and difficulty in completing the missed fasts at another time. A previous study found that Muslim women believed the only reason not to fast would be perceived harm to mother or fetus, but that fasting during pregnancy is safe for healthy women. Women feel strong spiritual, emotional, physical, and social benefits from fasting; it is seen as a way of maintaining cultural identity and unity among their communities (**Robinson et al., 2005**).

Many women asking their obstetrician if fasting is safe for their baby or not? There have been many studies on metabolic changes and different aspects of human health during and after Ramadan, but there have been few studies on the effect of fasting on pregnancy outcome and there are also some controversies in the findings of different studies (**Ziaee et al., 2006**).

Ramadan fasting during pregnancy is a controversial issue. A group of pregnant women do not fast due to the probable harmful effect on fetal health. Although Ramadan fasting may be postponed to the postnatal period, some pregnant women obey it as a religious activity (*Joosoph, 2004*).

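### IUGR is to be reported as an incidence, but nothing in the plan separates fetuses already growth-restricted at entry from new cases

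*Combined protocol and SAP*

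**What the plan says.** The secondary outcomes are given in the Sample Size Justification: "The secondary outcome measures are the incidence of unwanted fetal outcomes (e.g., IUGR, PTL, or NICU admission". IUGR has no stated threshold, no statement of whether it is diagnosed on scan or at birth, and no rule on time of onset.

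The Inclusion criteria cover maternal age, BMI and health ("Women included have no medical disorder") and gestation: "3rd trimester pregnancy (starting from 28 weeks) which is going to be calculated according to the date of the last menstrual period". No upper gestational limit is given. The Exclusion criteria are four: "History of systemic disorder", "Smoking narcotics or alcohol use", "Have previous history of fetal loss" and "Multiple pregnancies".

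Under Methodology, biometry, AFI and Doppler are measured every two weeks until delivery in women who have already met the eligibility criteria. Under Population, women are recruited from the clinic during Ramadan, followed, and then grouped by how much they fasted. Statistical Methods compares categorical outcomes by chi-squared or Fisher's exact test, with no adjustment for any baseline variable.

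**The concern.** A woman who enters at, say, 34 weeks with a fetus already growth-restricted meets every listed criterion. Her case is then counted as IUGR in whichever fasting group she ends up in, although fasting this Ramadan may have had nothing to do with it. Her baby also enters the birth-weight comparison, which is the primary outcome, and may add a NICU admission.

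Two consequences are possible. If such cases are spread evenly, they add the same background to each group and pull a true risk ratio towards 1. If they gather in the non-fasting group, the comparison is biased against finding harm. For a study that asks whether fasting worsens obstetric outcome, hiding harm is the more serious error.

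**Working it through.** **1. The plan's own figure.** For the secondary outcomes the plan states 93% power with N = 159, w = 0.3 and alpha 0.05. Three groups by yes/no gives 2 degrees of freedom, with noncentrality N × w² = 159 × 0.09 = 14.31. The noncentral chi-squared distribution gives 93.3%. The figure reproduces; this point is not about an arithmetic error.

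**2. Does any rule remove or separate pre-existing IUGR?**

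| Place in the plan | What it screens | Growth of the current fetus? |
|---|---|---|
| Inclusion: age, BMI, no medical disorder | Mother | No |
| Inclusion: third trimester | Gestation; ultrasound only confirms dates | No |
| Exclusion: systemic disorder, substance use | Mother | No |
| Exclusion: previous fetal loss | Past pregnancies | No |
| Exclusion: multiple pregnancy | Number of fetuses | No |
| Methodology: two-weekly scans | Follow eligibility; no rule uses the first one | No |
| Statistical Methods | Unadjusted tests | No |

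**3. Even spread (all inputs assumed).** Take 3 new cases of 53 in non-fasters and 9 of 53 in total fasters, a true ratio of 9/3 = 3.0. Add 8 pre-existing cases, 8/3 = 2.67 per group. The observed ratio is 11.67/5.67 = 2.1. With no true effect, the ratio stays at 1.0.

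**4. Uneven spread (all inputs assumed).** Let q be the overall proportion with IUGR at entry and s the share of those cases in the non-fasting group A. With equal groups:

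- pre-existing proportion in A: v = 3qs; in B and in C: v = 3q(1 − s)/2
- counted risk in a group: v + (1 − v) × new-case risk

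*No fasting effect, 5% new IUGR in every group:*

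| q | s | Counted risk in A | Counted risk in C | Ratio C/A |
|---|---|---|---|---|
| 2% | 1/3 | 6.9% | 6.9% | 1.0 |
| 2% | 50% | 0.03 + 0.97 × 0.05 = 7.9% | 0.015 + 0.985 × 0.05 = 6.4% | 0.82 |
| 6% | 80% | 0.144 + 0.856 × 0.05 = 18.7% | 0.018 + 0.982 × 0.05 = 6.7% | 0.36 |

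Across q = 2–6% and s = 50–80%, the chance of p < 0.05 with no true effect rises from 5% to between 6% and 53%.

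*True harm, new IUGR 5%, 10% and 15% in A, B and C:* the true C/A ratio of 3.0 is seen as 2.07 (q = 2%, s = 50%) down to 0.88 (q = 6%, s = 80%). Power for this scenario is 32% without pre-existing cases and between 9% and 21% with them.

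**5. A worked count (assumed).** Suppose 3 new cases in each group of 53 and 8 pre-existing cases split 5/2/1. The counts are 8/53 = 15.1%, 5/53 = 9.4% and 4/53 = 7.5%, against 3/53 = 5.7% in each group without them. Chi-squared is 1.71 on 2 degrees of freedom, p about 0.42. The estimate is distorted, but the planned test would not flag it.

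**The case against.** **Direction.** A reader might infer that pre-existing cases do gather in the non-fasting group. The documents do not say so. The nearest sentence, "A group of pregnant women do not fast due to the probable harmful effect on fetal health", describes fear of what fasting might do, not a fetal condition already diagnosed. The background's remark that women are exempt when fasting threatens the fetus is closer support, but it adds that many fast anyway. The mechanism also needs a problem the woman knows about: restriction first seen on the study scan cannot have shaped her earlier choice to fast. This objection stands, and direction is treated here as a possibility only.

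**Size.** Every prevalence and split above is assumed. If few fetuses are affected at entry, the effect is small. For birth weight, an assumed deficit of 600 g per affected baby with the 5/2/1 split shifts A against C by (5 − 1)/53 × 600 = about 45 g, roughly 0.1 SD if the SD is taken as 450 g. This also stands.

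**Timing.** A reader might infer that anything abnormal on the first scan preceded exposure and should be excluded. Recruitment is during Ramadan, so that scan may follow days of fasting. Removing low AFI or abnormal Doppler found on it could delete early effects of fasting, and only in the groups that fast; AFI is named as an outcome in the Aim of the Work. This stands and shapes the fix.

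**Definition comes first.** Pre-existing cases cannot be identified until IUGR is defined. That is true, and it is part of the same gap. The two-weekly scans would supply the data, but the plan does not say to use them this way.

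**Conclusion.** The gap holds. IUGR is called an incidence, and nothing in eligibility, outcome definition or analysis distinguishes cases present at entry from new ones, in groups that are self-selected and compared without adjustment. Pre-existing cases are therefore counted as outcomes of fasting. That much rests on the text alone.

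The size cannot be derived from the documents. Under the assumptions shown, the null ratio moves to between 0.82 and 0.36 if cases gather among non-fasters, stays at 1.0 if they spread evenly, and a true ratio of 3.0 is diluted to about 2.1 under the even-spread example. The documents do not support the stronger conclusions that the bias is large or that fasting will look protective. The point merits a change because the remedy is cheap, not because serious distortion has been shown.

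**What to change.** 1. Add an exclusion for IUGR documented before the woman's first fasting day of this Ramadan or, for non-fasters, before Ramadan began.
2. State the definition of IUGR. Name the first study scan as the baseline and record the number of days fasted before it.
3. Make new-onset IUGR after the baseline scan the incidence outcome. Leave cases present at that scan out of the denominator and report them by group.
4. As a sensitivity analysis, repeat the birth-weight and NICU comparisons without the cases present at baseline, or adjusted for baseline estimated fetal weight and gestational age.

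Do not exclude women for low AFI or abnormal Doppler first found on a scan done after fasting began.

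**Cost.** The scans are already planned; the additions are one exclusion line, one definition, one recorded count of days and one extra analysis. If 3–8% are affected (an assumption), 0.03 × 159 = 5 to 0.08 × 159 = 13 women leave the new-onset comparison. Starting from 180 recruited less 10% drop-out (162), that leaves 162 × 0.97 = 157 to 162 × 0.92 = 149, slightly below 159. At w = 0.3 and N = 149, noncentrality is 149 × 0.09 = 13.41 and power about 92%, so the loss is small on the plan's own terms; a few more recruits would cover it. Early effects of fasting already visible at the baseline scan would be reported separately, not as new cases.
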